#### **Follow-up Visit (Visit 4, Day 90 +/- 5 working days)**

- Inform patient that they are supposed to not take any study medication for the next 30 days but should continue their pain logs.
- Record adverse events as reported by participant to study co-ordinator. Study coordinator will ask about gastrointestinal health, any bleeding events and unusual bruising. PI will follow up with participant to assess the adverse events and determine whether to terminate participation.
- Record participant's adherence to treatment protocol.
- Inquire about any medication and health condition changes.
- Administer HRQoL instrument.
- Request participant to mail back or email their pain log and mail back any unused medication or email a photo of the empty bottle. The data from the pain logs will be compiled and analyzed at the start and end of each two treatment periods (on days 0, 90, 120, and 210).
- Ask participants about which medication, resveratrol or placebo, they think they were taking during the last 90 day period (evaluation of the success of blinding).
- Female participants in the United States will be asked to take a urine pregnancy test at local labcorp or local lab. Email a photo of self administered pregnancy test supplied by us for female international participants within 30 days prior to next medication mail out.
- Participants will be asked to complete blood draw to the closest LabCorp or from their local facility at our cost. For the International participants complete blood draw to the closest local facility blood and mailed to us for analysis at local Labcorp lab.
- The complete metabolic panel includes analysis of renal function [blood urea nitrogen (BUN), creatinine], liver function [total bilirubin, alanine aminotransferase (ALT), alkaline phosphatase (ALP), and aspartate aminotransferase (AST)], glucose, electrolytes [calcium, sodium, potassium, carbon dioxide (bicarbonate), chloride], protein [albumin, total protein]. The complete blood count (CBC) includes analysis of red blood count, hemoglobin, hematocrit, white blood cell count, platelet count. Platelet count below 50,000 per  $\mu$ l in CBC which indicates increased bleeding risk will result in removal from the study.

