## 5.4 PARTICIPANT WITHDRAWAL OR TERMINATION

### 5.4.1 REASONS FOR WITHDRAWAL OR TERMINATION

Participants are free to withdraw from the study at any time upon notification to the PI or study coordinator via phone or written request via email or postal mail An investigator may terminate participation in the study if:

- a. Any clinical adverse event (AE) or other medical condition or situation occurs such that continued participation in the study would not be in the best interest of the participant.
- b. The participant meets an exclusion criterion (either newly developed or not previously recognized) that precludes further study participation.

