### 5.4.2 HANDLING OF PARTICIPANT WITHDRAWALS OR TERMINATION

Participants who choose to withdraw or are withdrawn due to an AE or exclusion criteria must return the unused portion of study materials to the study coordinator. **All mailing/communication costs will be paid by the study.**

All participants withdrawn/discontinued will be followed for 1 month to make sure that no AEs have developed after withdrawal from the study. If a participant was withdrawn due to AEs, they will be advised to seek medical help with their primary care physician. Those costs are not covered by this study.

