### 7.3.3 FOLLOW-UP

#### **Follow-up Phone call (Visits 2, 3, 5, 6 and 7: Days 30, 60, 120, 150 and 180 +/- 5 working days)**

- Record adverse events as reported by participant to study co-ordinator. Study coordinator will ask about gastrointestinal health, any bleeding events and unusual bruising. PI will follow up with participant to assess the adverse events and determine whether to terminate participation.
- Record participant's adherence to treatment protocol.
- Inquire about any medication and health condition changes.
- Administer HRQoL instrument.
- Self-reported will be obtained from all study subjects using the Numeric Pain Rating Scale to score the subject's pain on a 0 to 10 scale. This scale has been validated and widely used. Pain will be ascertained daily (including during the "washout" period between the two intervention periods) through a daily pain log kept by participants. The pain logs will be requested from participants at each follow-up visit and at the end of each month in the treatment periods, and data from the pain logs will be compiled and analyzed at the start and end of each of the two treatment periods (on days 0, 90, 120, and 210).
- Request participant to mail back or email their pain log and a photo of the empty bottle at end of the month
- Inform participant to start on their next 30 days aliquot of study drug.

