7.3.7 SCHEDULE OF EVENTS TABLE

Visit type	Screening	Start 1 st arm	Follo w-up	Follo w-up	End 1 st arm	Wash out period	Start 2 nd arm	Follo w-up	Follo w-up	End of study	Post-study
Visit Number	0	1	2	3	4		5	6	7	8	9
Day		0	30	60	90		120	150	180	210	240

Procedures											
Check I/E criteria	X										
Obtain HIPAA clearance	X										
Informed Consent	X										
Obtain medical/medication history	X										
Urine pregnancy test	X					X					
Blood test	X					X				X	
HRQoL assessment		X	X	X	X		X	X	X	X	
Request pain logs			X	X	X		X	X	X	X	
Pain assessment (compile and analyze pain monthly average from pain logs)		X			X		X			X	
Request unused medication or photo of empty bottle			X	X	X			X	X	X	
SE/AE/SAE ascertainment			X	X	X		X	X	X	X	X
Query change in medications		X	X	X	X		X	X	X	X	
Query change in health status		X	X	X	X		X	X	X	X	
Blinding success evaluation					x					x	
Asked to start next month's dose		X	X	X			X	X	X		
Asked to stop taking all study drugs					X					X	

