#### 8.4.5 REPORTING OF PREGNANCY

Although resveratrol is likely to not have any untoward effect during pregnancy either to the mother or the fetus, there is no definitive data on the safety of the supplement during pregnancy. Therefore, pregnancy is considered an exclusion criteria in this study. During enrollment, female participants will be asked about their intention to get pregnant in the next few months. Additionally, female participants of child-bearing age will be asked to practice adequate contraception methods known to prevent pregnancy. They will be asked to notify the study team when they become pregnant and to stop study medication if such an event occurs. A urine pregnancy test will verify potential participants are not pregnant prior to test medication being mailed. A urine pregnancy test will be administered for participants in United States and International participants will self administer urine pregnancy test at the end of first 90 day period of placebo or resveratrol or during the 30 day washout period.

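### The only pregnancy test after screening may be done at Day 90 and is not tied to the first period-2 dose, so a conception in the washout can go untested before re-dosing

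*Combined protocol and SAP*

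**What the plan says.** Pregnancy is an exclusion criterion, as is childbearing age without adequate contraception (section 5.2). Section 8.4.5 expects no harm from resveratrol in pregnancy but acknowledges that conclusive safety data are lacking.

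Testing is described in these places:

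- **Entry (8.4.5):** "A urine pregnancy test will verify potential participants are not pregnant prior to test medication being mailed".
- **Between periods (8.4.5):** the test is to be done "at the end of first 90 day period of placebo or resveratrol or during the 30 day washout period".
- **Visit 4, Day 90 (7.3.3), US women:** "Female participants in the United States will be asked to take a urine pregnancy test at local labcorp or local lab". No limit relative to mailing or dosing is stated for them.
- **Visit 4, international women:** "Email a photo of self administered pregnancy test supplied by us for female international participants within 30 days prior to next medication mail out".
- **Schedule of events (7.3.7):** the row "Urine pregnancy test" is marked at screening and in the washout column, which carries no day number. Nothing is marked at Visit 5 (Day 120) or later.

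The procedure list that covers Visit 5 is shared with Visits 2, 3, 6 and 7 (7.3.3). It ends with "Inform participant to start on their next 30 days aliquot of study drug" and mentions neither a pregnancy test nor a result.

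The other safeguards are the monthly calls, which ask about pregnancy (7.1.1), the request that a woman report a pregnancy and stop study medication (8.4.5), and the investigator's power to end participation if "The participant meets an exclusion criterion (either newly developed or not previously recognized) that precludes further study participation" (5.4.1, item b).

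**The concern.** The test between periods matters mainly because it can stop a pregnant woman from starting a second 90-day course. Done at Day 90, it says nothing about the 30 days that follow. A woman who conceives in the washout and does not know it could answer the Day 120 questions truthfully, be told to start, and take study drug while pregnant, with every step compliant. Since the protocol already provides for this test, what matters is whether it falls where it protects most.

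**Working it through.** **Inputs.** Visit 4 is at Day 90 and Visit 5, the start of period 2, at Day 120 (7.3.3, 7.3.7). The washout is 30 days without medication (6.1.9). US supply arrives 5 days before the end of each 30-day period; international participants receive 90 days' supply (4.1, 6.1.10). Both visits have a window of ±5 working days.

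**The plan's own timeline.** 90 + 30 + 90 = 210 days, the stated participant duration. The gap from a Day 90 test to the start of period 2 is 120 − 90 = 30 days, the whole washout.

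**Visit windows.** Take 5 working days as at most 7 calendar days and let both visits move independently (assumptions). The gap then runs from (120 − 7) − (90 + 7) = 16 to (120 + 7) − (90 − 7) = 44 days.

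**International limit.** It bounds test to mailing, not test to dose. The largest test-to-dose gap is 30 days plus the time from mailing to first dose, which is not given. For an assumed 0, 5 or 14 days it is 30, 35 or 44 days.

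**Moving the test.** With a limit of L days before the start, the earliest test is Day 120 − L and the largest nominal gap is L.

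| L (days) | Earliest test | Gap shortened by |
|---|---|---|
| 3 | Day 117 | 30 − 3 = 27 days |
| 7 | Day 113 | 30 − 7 = 23 days |
| 10 | Day 110 | 30 − 10 = 20 days |

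**Detection lag.** A urine test does not turn positive at conception, and the documents give no lag. With a lag of g days, a test on day T can detect conceptions up to day T − g. Moving T from 90 to 113 shifts that date by (113 − g) − (90 − g) = 23 days, and moving it to 120 shifts it by 30 days. Both shifts are independent of g. The washout days covered, max(0, T − g − 90), do depend on it:

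| Assumed lag g | Day 90 test | Day 113 test | Day 120 test |
|---|---|---|---|
| 0 days | 0 of 30 | 23 of 30 | 30 of 30 |
| 7 days | 0 of 30 | 16 of 30 | 23 of 30 |
| 14 days | 0 of 30 | 9 of 30 | 16 of 30 |

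**What is given up.** US supply arrives at about 120 − 5 = Day 115 and is mailed earlier, so a test between Days 113 and 120 will usually follow mail-out. A pregnancy conceived in period 1 is found 113 − 90 = 23 to 120 − 90 = 30 days later than with a Day 90 test. No drug is taken in that interval.

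**The case against.** The strongest reply is that safeguards already exist and the fix trades one protection for another. Contraception is mandatory. Visit 5 is itself one of the monthly calls on which pregnancy is asked about, and its list includes health changes, so the question falls on the same call as the start instruction. The early-washout conceptions that a Day 113 test could find are also those most likely to be suspected by Day 120. The schedule already marks the washout column, so a late test is compliant today. A Day 90 test finds a period-1 exposed pregnancy sooner, at a visit where blood is drawn anyway, and the international rule ties the test to mailing; a late test gives both up.

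Much of this stands and keeps the point small. It does not remove it: the call relies on self-report and cannot find an unrecognised pregnancy, and a permitted late test is not a required one. The delay in finding a period-1 pregnancy carries no added exposure, because the washout is drug-free.

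A reader might infer two stronger claims that the documents do not support:

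- *That re-dosing is checked less strictly than entry.* The entry test is tied only to mailing, and the Day 0 call (7.3.2) lists no pregnancy result either. No internal standard is breached.
- *That a late test would cover most of the washout.* That depends on the lag. At 14 days, a Day 113 test covers 9 of 30 days.

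**Conclusion.** The point holds as a minor safety and scheduling matter. As written, the plan lets the only test after screening be done at Day 90, with a nominal 30 days to re-dosing and no result required at the start call. Women tested later in the washout already have a shorter gap. The gain from moving the test is a last detectable conception date 23 days later (Day 113) or 30 days later (Day 120). This follows from the calendar and assumes only that the lag is the same at either date. Very recent conceptions can still be missed.

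Those affected are the women of childbearing potential among the 30 planned participants, a number not stated. No endpoint, sample size or analysis changes. The 90 days on drug in each period remain without a scheduled test under either timing. The textual finding is firm; how many pregnancies the change would catch cannot be estimated from the documents.

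**What to change.** 1. In section 7.3.3 (Visit 4), the schedule of events (7.3.7) and section 8.4.5, set one timing for US and international women: late in the washout, as close to the Day 120 start as practical. Within 7 days is an example; the documents give no figure.
2. In the follow-up list in 7.3.3, add a line for Visit 5 only: a negative result is confirmed before the start instruction. A woman with a positive result does not start and returns the drug. Section 5.4.2 already says that participants withdrawn on exclusion criteria "must return the unused portion of study materials to the study coordinator".

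The cost is wording in four places, with the same number of tests and no extra outbound shipment. The downsides are:

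- The start call replaces mail-out as the checkpoint, so a pregnant woman may already hold drug (up to 90 days' supply if international), and a return paid for by the study may be needed.
- A period-1 pregnancy is found 23 to 30 days later, off drug.
- US women may need a laboratory trip separate from the Visit 4 blood draw.
- Visit 5 may slip by a few days while a result is awaited.

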7.3.4 FINAL STUDY VISIT

**Final Study Visit (Visit 8, Day 210 +/- 5 working days)**

- Inform patient that they have completed the study.
- Record adverse events as reported by participant to study co-ordinator. Study coordinator will ask about gastrointestinal health, any bleeding events and unusual bruising. PI will follow up with participant to assess the adverse events and determine whether to terminate participation.
- Record participant’s adherence to treatment protocol.
- Inquire about any medication and health condition changes.
- Participants will be asked to complete blood draw from their local facility at our cost to assess kidney function, liver function and blood cell count. The complete metabolic panel includes analysis of renal function [blood urea nitrogen (BUN), creatinine], liver function [total bilirubin, alanine aminotransferase (ALT), alkaline phosphatase (ALP), and aspartate aminotransferase (AST)], glucose, electrolytes [calcium, sodium, potassium, carbon dioxide (bicarbonate), chloride], protein [albumin, total protein]. The complete blood count (CBC) includes analysis of red blood count, hemoglobin, hematocrit, white blood cell count, platelet count. Platelet count below 50,000 per µl in CBC which indicates increased bleeding risk will result in removal from the study.
- Administer HRQoL instrument.
- Request participant to mail back or email their pain log and mail back any unused medication or email a photo of the empty bottle. The data from the pain logs will be compiled and analyzed at the start and end of the two treatment periods (on days 0, 90, 120, and 210).
- Ask participants about which medication, resveratrol or placebo, they think they were taking during the last 90 day period (evaluation of the success of blinding).

**Post Study Visit (Visit 9, Day 240 +/- 5 working days)**

- Participants will be queried regarding any AE/SAE.

7.3.5 EARLY TERMINATION VISIT

If the study terminates early, the participants will be called and notified of study termination. In addition, the call will include the following:

- Information will be collected on any adverse events that the subjects may have experienced during their participation in the study. If the participant reports any adverse events, especially if they were the reason for early termination, the participant will be advised to seek medical assistance from their primary care physician.
- Participants will be asked to mail back any unused medication or email a photo of the empty bottle. Participants will be asked to mail back or email their pain log.
- HRQoL will be administered.
- Participants will be informed that they will be re-contacted 30 days post-termination visit to assess any AE/SAE.

7.3.7 SCHEDULE OF EVENTS TABLE

Visit type	Screening	Start 1 st arm	Follo w-up	Follo w-up	End 1 st arm	Wash out period	Start 2 nd arm	Follo w-up	Follo w-up	End of study	Post-study
Visit Number	0	1	2	3	4		5	6	7	8	9
Day		0	30	60	90		120	150	180	210	240

Procedures											
Check I/E criteria	X										
Obtain HIPAA clearance	X										
Informed Consent	X										
Obtain medical/medication history	X										
Urine pregnancy test	X					X					
Blood test	X					X				X	
HRQoL assessment		X	X	X	X		X	X	X	X	
Request pain logs			X	X	X		X	X	X	X	
Pain assessment (compile and analyze pain monthly average from pain logs)		X			X		X			X	
Request unused medication or photo of empty bottle			X	X	X			X	X	X	
SE/AE/SAE ascertainment			X	X	X		X	X	X	X	X
Query change in medications		X	X	X	X		X	X	X	X	
Query change in health status		X	X	X	X		X	X	X	X	
Blinding success evaluation					x					x	
Asked to start next month's dose		X	X	X			X	X	X		
Asked to stop taking all study drugs					X					X	

**7.4 JUSTIFICATION FOR SENSITIVE PROCEDURES**

NA

**7.5 CONCOMITANT MEDICATIONS, TREATMENTS, AND PROCEDURES**

None

**7.5.1 PRECAUTIONARY MEDICATIONS, TREATMENTS, AND PROCEDURES**

None

**7.6 PROHIBITED MEDICATIONS, TREATMENTS, AND PROCEDURES**

Current use of resveratrol at time of study start (Day 0). Use of NSAIDs or aspirin. Blood thinners, lovastatin, ketoconazole, itraconazole, fexofenadine and triazolam. Alfentanil, Cyclosporine, Dihydroergotamine, Dofetilide, Ergotamine, Fentanyl, Flibanserin, Oxycodone, Pimavanserin, Pimozide, Quinidine, Saquinavir, Sirolimus, Tacrolimus, Temsirolimus, Theophylline, Tizanidine, Thioridazine, Fosphenytoin, Phenytoin or Warfarin.

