## 4 STUDY DESIGN AND ENDPOINTS

### 4.1 DESCRIPTION OF THE STUDY DESIGN

The study has a 2x2 crossover design. Participants will take either the placebo or resveratrol for 90 days followed by a 30 day washout period and the placebo or resveratrol for the last 90 days. 30 day washout period was chosen in order to eliminate any carry over from resveratrol as it is recommended to avoid resveratrol 2 weeks prior to surgery suggesting that carry over could potentially be as long as 2 weeks (<http://www.webmd.com/vitamins-supplements/ingredientmono-307-resveratrol.aspx?activeingredientid=307>; <http://ww5.komen.org/BreastCancer/Resveratrol.html>). Participants will be mailed a 30 or 90 day (for international participants) supply of placebo or resveratrol which they will receive 5 days before the end of each 30 day period (not applicable for international participants). Participants will keep daily pain log of pain and activity levels during the entire 210 day study period. We recognize that this is a long period of time however this population is highly motivated because 1) their pain is not systematically treated, 2) currently available over the counter NSAIDs, frequently used to control pain, cause gastrointestinal issues when used for prolonged periods and 3) participants reached through Little People of America and the PSACH facebook page are actively seeking solutions to control pain. This is being co-ordinated by a single center and will enroll 30 PSACH individuals. Because this is a rare condition, participants from 18 years - to 70 years will be enrolled.

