### 5.2 PARTICIPANT EXCLUSION CRITERIA

1. Current use of resveratrol
2. Current use of blood thinners, lovastatin, ketoconazole, itraconazole, fexofenadine and triazolam.
3. Other non-PSACH related health conditions, e.g. cancers.
4. Pregnancy or breastfeeding.
5. Women of childbearing age not using adequate contraception methods known to prevent pregnancy during the study.
6. Participation in another clinical study and/or using investigational agents.
7. Use of NSAIDs or aspirin.
8. Current use of Alfentanil, Cyclosporine, Dihydroergotamine, Dofetilide, Ergotamine, Fentanyl, Flibanserin, Oxycodone, Pimavanserin, Pimozide, Quinidine, Saquinavir, Sirolimus, Tacrolimus, Temsirolimus, Theophylline, Tizanidine, Thioridazine, Fosphenytoin, Phenytoin or Warfarin.
9. Age 17 years or less.
10. Platelet count below 50,000 per  $\mu\text{l}$  on baseline CBC.

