## 7 STUDY PROCEDURES AND SCHEDULE

### 7.1 STUDY PROCEDURES/EVALUATIONS

#### 7.1.1 STUDY SPECIFIC PROCEDURES

- All potential participants will submit photos to confirm their PSACH diagnosis either by directly depositing photos into a secured encrypted server or via US mail (to be scanned and put into our secure data base and subsequently shredded).
- Medical history will be obtained by interview to confirm diagnosis of PSACH and to exclude those taking exclusion medications resveratrol, blood thinners, lovastatin, ketoconazole, itraconazole, fexofenadine, triazolam, Alfentanil, Cyclosporine, Dihydroergotamine, Dofetilide, Ergotamine, Fentanyl, Flibanserin, Oxycodone, Pimavanserin, Pimozide, Quinidine, Saquinavir, Sirolimus, Tacrolimus, Temsirolimus, Theophylline, Tizanidine, Thioridazine, Fosphenytoin, Phenytoin, or Warfarin. This information will be ascertained by the study staff over the phone and the participants will be asked to read the names of the medications and the dosages off the medicine containers. Information on medications will be collected for All medications the participant is on (both prescription and OTC). Exclusions will be made if any of the medications mentioned above are being used.
- Pain will be assessed to ensure that participants have pain to enroll in the study.
- For this 2X2 crossover design with two periods, patients will be randomized to one of two sequences, resveratrol/placebo or placebo/resveratrol. Those randomized to resveratrol/placebo will be given resveratrol in the first period and placebo in the second and vice versa for those randomized to the placebo/resveratrol sequence. Randomization will be carried out by our biostatistician so that investigators evaluating outcomes, along with participants, are blinded.
- Once enrolled into the study and randomized, a parcel will be mailed to the participants including all study materials including first month's study drug supply, study forms and pain logs.
- Monthly phone calls will be used to assess of adherence to protocol and will be logged into the study logbook by study staff. These phone calls will also include ascertainment of any changes to medications and diagnosis of any new health condition or pregnancy.
- Patient-reported daily pain logs will be mailed or emailed to study co-ordinator on a monthly basis.

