7.3.2 ENROLLMENT/BASELINE

**Baseline Phone call (Visit 1, Day 0)**

- Patient will be contacted after receipt of initial study package via postal mail (including medications and information for blood draw to assess kidney function, liver function and blood cell count). The complete metabolic panel includes analysis of renal function [blood urea nitrogen (BUN), creatinine], liver function [total bilirubin, alanine aminotransferase (ALT), alkaline phosphatase (ALP), and aspartate aminotransferase (AST)], glucose, electrolytes [calcium, sodium, potassium, carbon dioxide (bicarbonate), chloride], protein [albumin, total protein]. The complete blood count (CBC) includes analysis of red blood count, hemoglobin, hematocrit, white blood cell count, platelet count. Platelet count below 50,000 per  $\mu\text{l}$  in CBC which indicates increased bleeding risk will result in exclusion.
- For Participants in the United States they will be asked to complete blood draw to the closest LabCorp or from their local facility at our cost. For the International participants blood need to be draw from a local facility an mailed to us for analysis at the local labcorp lab.

- Query participants about any changes in inclusion/exclusion criteria.
- Patients will be asked to start taking study medication on the next day.
- Administer HRQoL instrument.

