## 7.9 PARTICIPANT ACCESS TO STUDY AGENT AT STUDY CLOSURE

Since resveratrol reserveage is an over-the-counter supplement, patients will have full access to product after study concludes.

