### 10.4.2 ANALYSIS OF THE PRIMARY EFFICACY ENDPOINT(S)

A baseline pain assessment will take place at the first visit (day 0). Pain will then be ascertained daily (including during the "washout" period between the two intervention periods) through a daily pain log kept by participants. The pain logs will be requested from participants at each follow-up visit and at the end of each month in the treatment periods, and data from the pain logs will be compiled and analyzed at the start and end of each of the two treatment periods (on days 0, 90, 120, and 210). Each of these scores will then be entered as raw values for each subject if the parameter distribution is non-normal, ranked values will be used as units of analysis.

The primary endpoint will be change in pain score between baseline and monthly average pain score. The pain score on each day of month one will averaged to obtain the average pain score for month one, and the same will be done

for months two and three, and each of the monthly average scores for resveratrol and placebo periods will be compared to baseline.

In an extreme condition, if a sufficiently large proportion (>30%) of the study subjects experience no pain (a score of 0), zero-inflated negative binomial models will be utilized to analyze the data while considering the individuals that report no pain.

---

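### Resveratrol is barred only as current use at Day 0: no time off is required before baseline, and outside use is not expressly prohibited later, although the plan requires a 30-day washout between periods

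*Combined protocol and SAP*

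**What the plan says.** The combined protocol and SAP restricts resveratrol in three places, each time as present use.

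- Section 5.2, exclusion 1: "Current use of resveratrol", with no look-back interval.
- Section 7.1.1, screening interview on all prescription and over-the-counter medications: "Exclusions will be made if any of the medications mentioned above are being used".
- Section 7.6, prohibited list: "Current use of resveratrol at time of study start (Day 0"). Resveratrol is the only item there tied to Day 0; the other listed drugs carry no time limit.

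On carry-over, section 4.1 states: "30 day washout period was chosen in order to eliminate any carry over from resveratrol". It reasons from advice on stopping before surgery that "carry over could potentially be as long as 2 weeks".

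On timing, section 10.4.2 states: "A baseline pain assessment will take place at the first visit (day 0"). The Day 0 call in section 7.3.2 adds: "Patients will be asked to start taking study medication on the next day". The primary endpoint is the change from baseline to the average pain score of each treatment month (4.2.1, 10.4.2).

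At Day 90 (7.3.3) participants are told to stop study medication for 30 days. The instruction does not mention resveratrol from other sources.

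**The concern.** The protocol treats residual resveratrol as a threat to Period 2 and sets aside 30 days to remove it. It sets aside none before Period 1, although the Day 0 baseline and the first month of treatment are open to the same carry-over.

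The wording of 7.6 adds a second gap. A bar tied to Day 0 does not, on its face, forbid a participant from buying resveratrol during the placebo period or the washout, and no other section does so expressly. Section 2.2 notes that the product is sold over the counter, and 4.1 describes the people to be recruited as looking for ways to manage their pain.

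What is at stake is the resveratrol-placebo difference. Resveratrol taken during placebo, or carried over into placebo days, makes the two conditions more alike and dilutes that difference.

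**Working it through.** The plan gives no figure for this point, so there is none to reproduce. The inputs are a possible carry-over of 14 days and a 30-day washout (4.1), 30-day months within a 90-day period (4.2.1, 6.1.9), baseline on Day 0 with dosing from the next day (10.4.2, 7.3.2), and 30 participants (4.1). The documents give no rate of past or concurrent resveratrol use, so I assume a share p of 10-30%.

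**1. Ceiling for one participant.** If someone stopped g days before Day 0, the carry-over days left in Period 1 are max(0, 14 − g).

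| g (days) | Share of month one | Share of 90-day period |
|---|---|---|
| 0 | 14/30 = 47% | 14/90 = 16% |
| 7 (half the bound) | 7/30 = 23% | 7/90 = 8% |
| 14 or more | 0% | 0% |

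The documents do not state g. The first row is the maximum.

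**2. Average over the trial.** Carry-over from before entry can reach placebo days only in the placebo-first sequence. Assume equal allocation, recent users spread evenly over the sequences, and g = 0 for all of them. The affected share of all month-one placebo days is 0.5 × p × 14/30:

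- p = 10%: 0.5 × 0.10 × 14/30 = 2.3%
- p = 30%: 0.5 × 0.30 × 14/30 = 7.0%

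Over 90 days, 0.5 × p × 14/90 gives 0.8% to 2.3%.

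**3. Direction of the baseline distortion.** Let R and P be the pain averages on resveratrol and placebo, B0 and B120 the true pain levels at Days 0 and 120, and e the error that carry-over adds to the Day 0 score (e < 0 if resveratrol lowers pain). A negative resveratrol-minus-placebo difference means benefit.

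- One baseline for both periods: (R − B0 − e) − (P − B0 − e) = R − P. The error cancels.
- A baseline for each period, placebo first: (R − B120) − (P − B0 − e) = (R − B120) − (P − B0) + e. Benefit is overstated.
- A baseline for each period, resveratrol first: (R − B0 − e) − (P − B120) = (R − B0) − (P − B120) − e. Benefit is understated.

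Under randomisation the last two offset on average, though not necessarily in a sample of 30.

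**4. Outside use during placebo.** Suppose a share p takes an equally effective product throughout placebo and stays in the analysis. Those participants show no difference, so the mean difference becomes (1 − p) times its true value. At the same SD, the required sample size rises by 1/(1 − p)².

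| p (assumed) | Difference shrinks by | Required N multiplied by | 30 participants are worth |
|---|---|---|---|
| 10% | 10% | 1/0.90² = 1.23 | 30 × 0.81 = 24 |
| 20% | 20% | 1/0.80² = 1.56 | 30 × 0.64 = 19 |
| 30% | 30% | 1/0.70² = 2.04 | 30 × 0.49 = 15 |

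**The case against.** The strongest reply is that the plan already controls much of this.

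**Entry.** Medication use is reviewed at screening (7.1.1, 7.3.1). The parcel is mailed only after enrolment and randomisation, the Day 0 call follows its receipt, and eligibility is queried again on that call (7.3.2). A reader might infer that someone can routinely stop the day before Day 0 and still enter. The documents do not support that, because such a person would normally have been a current user at screening and so excluded. This stands, and it makes 47% a ceiling. It does not supply a required interval: the time from screening to Day 0 is unspecified, and no question about past use is laid down.

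**Later use.** Medication changes are queried at each visit from Day 0 to Day 210 (7.3.2 to 7.3.4, 7.3.7). Under 5.4.1(b) the investigator can end participation when an exclusion criterion is newly met. It would therefore be wrong to say that later use is uncontrolled. But a query detects rather than prohibits, the termination is discretionary and follows exposure, and neither tells participants to avoid outside resveratrol.

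**Bias.** A reader might infer that every route pushes toward no effect. That holds for resveratrol acting on placebo days, but not for the baseline (step 3).

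**Evidence.** Section 7.9 says "Since resveratrol reserveage is an over-the-counter supplement, patients will have full access to product after study concludes". This shows availability but concerns the time after the trial. No section reports actual use in this population, and the 2-week figure comes from surgical advice rather than from data on pain.

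**Conclusion.** The concern holds as a gap in the stated rules. The test substance has the narrowest time limit on the prohibited list, and the protocol's own carry-over reasoning is applied between periods but not at entry.

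The missing look-back is the better-documented half, but its likely effect is small: about 2-7% of month-one placebo days if 10-30% of participants are recent users who all stopped right at Day 0, and less if they stopped sooner. The missing bar on later use could matter more, with a 10-30% loss of the treatment difference if the same share took an equally effective product throughout placebo, undetected. Both ranges rest on assumed usage rates and show sensitivity, not expected bias. The documents do not show that contamination will occur, or at what rate.

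The sponsor should correct this because the effect could be material and the change is cheap.

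**What to change.** Reconcile 5.2 item 1, 7.6 and the Day 90 instruction in 7.3.3 with 4.1:

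- In 5.2 item 1, apply the protocol's own between-period washout interval as a look-back before Day 0, covering resveratrol and supplements that contain it, and allow re-screening once the interval has passed. Match the screening question in 7.1.1.
- In 7.6, replace the Day 0 wording with a bar on any resveratrol other than study product through Day 210, including the washout, and repeat it in the Day 90 instruction.
- Name resveratrol in the existing monthly medication query.

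The cost is a few lines of text and one named question in calls already scheduled. The downside is that a few recent users would start later, by up to the length of the washout interval.
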